**NCT Number:**

## **Efficacy Of Nasal Irrigation With Combination of 0.9% NaCl and Binahong Extract (*Anredera Cordifolia*) 2,5% In Allergic Rhinitis**

### **Background**

The current management of RA includes education, reducing exposure to allergens, pharmacology, immunotherapy, and complementary (Linton et al., 2021). Clinical practice therapy guidelines were developed on Allergic Rhinitis and its Impact on Asthma (ARIA) through integrated social media, mobile health, and multidisciplinary services (Bousquet et al., 2019; Zhang et al., 2021). According to ARIA recommendations, therapy aims to control the symptoms that arise. However, 20% more patients are still symptomatic even though they have received adequate therapy according to treatment guidelines. To overcome this problem, in the 20th century, personalized medicine developed a therapeutic method that adapts individual patient characteristics with a genetic basis, immunology, and bio-psycho-social profiles as a dynamic process (Licari et al., 2019). This therapeutic approach aims to minimize side effects, increase therapeutic success, and develop into precision medicine. The target of therapy that is currently being developed is to modify the immune response to allergens and prevent disease development with a preventive approach, namely at the beginning of the process when the allergen attaches to the nasal mucosa (Agache & Akdis, 2019; Dubey et al., 2019).

A study of the 0.3% Binahong extract combination, which has an anti-inflammatory effect on 0.9% NaCl nasal wash therapy in adult allergic rhinitis patients, has never been done before. There is a potential role, together with physical and immunological mechanisms, to increase the efficacy of nasal washing. Based on the explanation above, it is necessary to research to determine the effect of a combination of 3% Binahong extract as a herbal medicine to increase the results of 0.9% NaCl nasal wash by assessing mRNA expression (IL-4, IL-6, IL-13, and TNF- $\alpha$ ) as the primary outcome. Besides that, secondary outcome assessments are still carried out in clinical symptoms, quality of life, and nasal physiology, which researchers usually do to assess treatment in allergic rhinitis patients. Hopefully, this research will become a source of allergic rhinitis therapy and support the independence of drugs with natural ingredients.

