## Methods

This study was designed with the Consolidated Standards of Reporting Trials (CONSORT) guidelines by clearly stating the items that must be informed in RCT research reports to avoid bias. The research flow process will follow the flowchart guidelines of the enrollment, allocation, follow-up, and analysis phases (Schulz et al., 2011). This research is a quantitative experimental study with a single-blind parallel randomized controlled trial design to determine the results of intervention for 0.9% NaCl nasal irrigation therapy added with 3% Binahong extract compared to the control group 0.9% NaCl nasal irrigation therapy for two weeks in adult RA sufferers, which are schematically described as follows:

[figure not shown]

Figure 1. Research Design

Information:

P = Population

S = Sample

R = randomization of allocations

O1 = Examination before treatment

O2 = Examination before treatment

O3 = Examination after treatment

O4 = Examination after treatment

K = NaCl 0.9% nasal irrigation control

P = 0.9% NaCl nasal irrigation + 3% Binahong Extract

The process of randomization to allocate participants to the intervention group or control group was carried out using random numbers generated by a computer program and statistical software with an allocation of 1:1. The random number results were entered into sealed envelopes using the SNOSE (sequentially numbered, opaque sealed envelopes) system. Participants were assigned to the intervention or control group based on the order of randomization (allocation concealment) carried out by the research assistant and given a 0.9% NaCl nose irrigation pack plus 3% Binahong extract (freeze drying) or a 0.9% NaCl nose irrigation pack for two weeks. The investigators needed access to the blinding group's sequences, and the entire study team was instructed not to communicate with participants about their sequences.

The research sample was RA patients at the AMC Muhammadiyah General Hospital Polyclinic and PKU Muhammadiyah Gamping Hospital Yogyakarta who met the inclusion and exclusion criteria as follows:

1. Inclusion criteria
  - a. Patients with RA symptoms (SFAR score  $\geq 7$ ) (Widuri A, 2021), adult age (18 to 65 years), male or female
  - b. SPT examination results are positive
  - c. Agree to participate in the research (informed consent) in writing
2. Exclusion criteria
  - a. Pregnant or breastfeeding women
  - b. Active smoker
  - c. Local allergic rhinitis

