  - d. Patients with autoimmune diseases
  - e. Chronic rhinosinusitis with or without nasal polyps

The number of samples in this study was determined using the sample size formula for research that aims to determine the change in the average (mean) before and after the intervention of the two paired groups tested with paired t-test. The variables to be examined in this study are:

1. Independent variable: nasal washing treatment with 0.9% NaCl + 3% concentration of Binahong Extract or control nasal washing with 0.9% NaCl.

NCT Number:  
13 March 2023

2. Dependent variables: mRNA expression (IL-4, IL-6, IL-13, and TNF- $\alpha$ ), SNOT-22, Mini-RQLQ, Nasal flow and Patency, and Mucociliary Transport Time.
3. Control variables: gender, classification.

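### Does naming four cytokine mRNAs as one primary outcome, with no stated success rule, inflate the false-positive rate?

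*Protocol*

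**What the plan says.** The Background states that the effect of adding Binahong extract to saline irrigation will be judged "by assessing mRNA expression (IL-4, IL-6, IL-13, and TNF"-alpha) "as the primary outcome. Besides that, secondary outcome assessments are still carried out". The secondary outcomes that follow are clinical symptoms, quality of life and nasal physiology.

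The list of dependent variables in Methods repeats the four cytokines and then adds "SNOT-22, Mini-RQLQ, Nasal flow and Patency, and Mucociliary Transport Time". It does not rank the cytokines.

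The sample-size sentence in Methods describes a generic formula for a change in a mean in "the two paired groups tested with paired t-test". It names no outcome variable. Randomisation is "with an allocation of 1:1".

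The protocol gives no significance level, no sidedness, no power, no sample size, no named test comparing the arms on a cytokine, and no definition of a positive trial.

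**The concern.** The label is singular but the variables are four. If each cytokine is tested at the usual level and any significant one is reported as the primary result, the trial has four chances of a false claim. A reader of the final report could not then tell a prespecified primary result from the best of four.

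The sample-size sentence sharpens the worry. It speaks of one mean change, and the number of patients needed depends on whether one cytokine suffices or all must succeed. At stake is whether a positive primary claim carries the nominal 5% error rate or one nearly four times as large.

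**Working it through.** The protocol states no error rate, so there is no figure of its own to reproduce. The check is what each possible success rule would imply.

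**Inputs**
- Number of primary variables: 4 (Background).
- Level per test: not stated. Assumed two-sided 0.05, with 0.01 to 0.10 as the range.
- Correlation among the four test statistics: not stated. Assumed equal for all pairs, from 0 to 0.9.

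**Rule A: any one significant, no adjustment**
- Independent tests: 1 − (1 − 0.05)^4 = 1 − 0.8145 = 0.1855, or 18.5%.
- Bound with no assumption on dependence: 4 × 0.05 = 20%.
- Counting only false claims in the extract's favour, independent tests: 1 − 0.975^4 = 9.6%, against 2.5% for a single test.

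A simulation of four equally correlated normal statistics (1,000,000 draws, each tested at two-sided 0.05, all nulls true) gives:

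| Correlation | Any one significant | All four significant |
|---|---|---|
| 0 | 18.6% | 0.0006% |
| 0.3 | 17.3% | 0.02% |
| 0.5 | 15.6% | 0.15% |
| 0.7 | 13.0% | 0.57% |
| 0.9 | 9.4% | 1.9% |

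The assumed level matters as much as the correlation. Under independence:
- 0.01 per test: 1 − 0.99^4 = 3.9%
- 0.025 per test: 1 − 0.975^4 = 9.6%
- 0.10 per test: 1 − 0.90^4 = 34.4%

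**Rule B: all four significant, each at 0.05**
The right-hand column of the table applies when all four nulls are true. In general the rate cannot exceed 5%, because a false claim requires rejecting at least one true null at 0.05.

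**Rule C: any one significant, with Bonferroni or Holm**
The first threshold is 0.05 / 4 = 0.0125. The familywise rate is at most 4 × 0.0125 = 5%; for Bonferroni with independent tests it is 1 − 0.9875^4 = 4.9%.

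**Comparison with the text**
Only Rule A inflates the error, and only without adjustment. The Background and Methods contain no sentence that adopts Rule A, B or C. The 18.5% is therefore a property of a rule brought from outside, at a level brought from outside. Because the secondary outcomes are listed separately, the primary family is limited to the four cytokines.

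**Sample size**
The rule does affect the size of the trial:
- For a single cytokine, moving from 0.05 to 0.0125 multiplies the sample size by ((2.498 + 0.842) / (1.960 + 0.842))^2 ≈ 1.42 at 80% power, and by about 1.36 at 90%.
- Under Rule B, four independent tests with 80% power each (assumed) would all succeed with probability 0.8^4 = 41%; positive correlation would raise this.

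Neither result contradicts the protocol, which gives no sample size, level or power to compare with. The formula is not tied to any variable, so the text fits a separate calculation for each cytokine as well as a single calculation.

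**The case for a change.** The strongest case for a change is that the choice of primary outcome, and the result that would meet the objective, belong in the protocol itself. On this view the protocol took the matter up and settled it badly, by giving one label to four variables. Adding a rule later is also not free, as the sample-size factors show. Even at a correlation of 0.9 the unadjusted any-one rate is about 9.4%, nearly double 5%, and naming a rule would take only a sentence or two.

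Part of this stands. The combining rule is not in the protocol, a reader cannot infer it, and it has to be settled before outcome data are looked at by arm.

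The rest does not follow. The endpoints themselves are named and kept apart from the secondary ones, and having several primary variables is not in itself an error. What is absent is the rule for combining them and any division of alpha, which is ordinary content for a statistical analysis plan. It also goes too far to say that the protocol lets any single significant cytokine carry the claim, or that it sizes the trial as though four tests were one. The text says neither.

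**Conclusion.** The concern does not call for a change. The arithmetic is right but conditional: 18.5% requires a per-test level of 0.05, independence, and an unadjusted any-one rule, and the protocol states none of the three. With the 0.05 level and the any-one rule kept, the rate runs from about 9.4% (correlation 0.9) to 18.5%, with 20% as the bound under any dependence. Under an all-four rule, or Holm across the four, it is at most 5%.

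What remains is a gap in detail. The protocol names four primary variables and leaves open how they combine, which a statistical analysis plan commonly fills. That document may exist and has not been seen, so its silence cannot be assumed. The conclusion would differ if an analysis plan did adopt an unadjusted any-one rule; the protocol alone gives no ground for saying so.

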## Methods

This study was designed with the Consolidated Standards of Reporting Trials (CONSORT) guidelines by clearly stating the items that must be informed in RCT research reports to avoid bias. The research flow process will follow the flowchart guidelines of the enrollment, allocation, follow-up, and analysis phases (Schulz et al., 2011). This research is a quantitative experimental study with a single-blind parallel randomized controlled trial design to determine the results of intervention for 0.9% NaCl nasal irrigation therapy added with 3% Binahong extract compared to the control group 0.9% NaCl nasal irrigation therapy for two weeks in adult RA sufferers, which are schematically described as follows:

[figure not shown]

Figure 1. Research Design

Information:

P = Population

S = Sample

R = randomization of allocations

O1 = Examination before treatment

O2 = Examination before treatment

O3 = Examination after treatment

O4 = Examination after treatment

K = NaCl 0.9% nasal irrigation control

P = 0.9% NaCl nasal irrigation + 3% Binahong Extract

The process of randomization to allocate participants to the intervention group or control group was carried out using random numbers generated by a computer program and statistical software with an allocation of 1:1. The random number results were entered into sealed envelopes using the SNOSE (sequentially numbered, opaque sealed envelopes) system. Participants were assigned to the intervention or control group based on the order of randomization (allocation concealment) carried out by the research assistant and given a 0.9% NaCl nose irrigation pack plus 3% Binahong extract (freeze drying) or a 0.9% NaCl nose irrigation pack for two weeks. The investigators needed access to the blinding group's sequences, and the entire study team was instructed not to communicate with participants about their sequences.

The research sample was RA patients at the AMC Muhammadiyah General Hospital Polyclinic and PKU Muhammadiyah Gamping Hospital Yogyakarta who met the inclusion and exclusion criteria as follows:

1. Inclusion criteria
  - a. Patients with RA symptoms (SFAR score  $\geq 7$ ) (Widuri A, 2021), adult age (18 to 65 years), male or female
  - b. SPT examination results are positive
  - c. Agree to participate in the research (informed consent) in writing
2. Exclusion criteria
  - a. Pregnant or breastfeeding women
  - b. Active smoker
  - c. Local allergic rhinitis
  - d. Patients with autoimmune diseases
  - e. Chronic rhinosinusitis with or without nasal polyps

The number of samples in this study was determined using the sample size formula for research that aims to determine the change in the average (mean) before and after the intervention of the two paired groups tested with paired t-test. The variables to be examined in this study are:

1. Independent variable: nasal washing treatment with 0.9% NaCl + 3% concentration of Binahong Extract or control nasal washing with 0.9% NaCl.

NCT Number:  
13 March 2023

2. Dependent variables: mRNA expression (IL-4, IL-6, IL-13, and TNF- $\alpha$ ), SNOT-22, Mini-RQLQ, Nasal flow and Patency, and Mucociliary Transport Time.
3. Control variables: gender, classification.

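### Two recruiting hospitals, but the described allocation is not stratified by hospital and hospital is not a control variable: avoidable chance imbalance and lost precision (minor)

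*Protocol*

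**What the plan says.** All the relevant text is in the Methods section of the protocol.

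- **Recruitment.** Two sites are named: "The research sample was RA patients at the AMC Muhammadiyah General Hospital Polyclinic and PKU Muhammadiyah Gamping Hospital Yogyakarta".
- **Sequence.** Allocation uses "random numbers generated by a computer program and statistical software with an allocation of 1:1". No stratification factor or block scheme is given.
- **Concealment.** The numbers were "entered into sealed envelopes using the SNOSE (sequentially numbered, opaque sealed envelopes) system", and participants were assigned "based on the order of randomization (allocation concealment) carried out by the research assistant". The text does not say whether there is one envelope set or one per hospital.
- **Variables to control.** The list reads "Control variables: gender, classification". Hospital is not on it.
- **Sample size.** The formula is described as one for the "change in the average (mean) before and after the intervention of the two paired groups tested with paired t-test", but no total, effect size or SD follows.

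**The concern.** When patients come from two hospitals, hospital is a factor that the recruitment plan itself creates. Case mix and response to treatment may differ between the sites. The protocol takes the step of naming factors to be controlled and leaves this one out, both from the allocation procedure and from the control list.

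Two things are at stake. First, nothing in the described allocation keeps the arms balanced within each hospital. In a small trial, one arm may by chance draw noticeably more of its patients from one site, and part of an observed difference between arms could then reflect hospital. Second, if hospital is not in the comparison, whatever outcome variation lies between hospitals is counted as noise, and the confidence interval is wider than it need be.

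Stratification has to be settled before the first envelope is opened. An analysis plan can add a covariate later, but it cannot restore balance within hospitals.

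**Working it through.** The protocol states no figure to reproduce. The total sample size, the split between hospitals and the size of any hospital effect are all assumptions below. Only the two hospitals, the 1:1 ratio and the control list come from the protocol.

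**Chance imbalance.** Let N be the total, with N/2 per arm and N/2 at each hospital. Under unstratified allocation with equal arms, the number x of first-hospital patients in the extract arm is hypergeometric. The between-arm difference in hospital share is d = x/(N/2) − (N/2 − x)/(N/2).

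For N = 40, P(x) = C(20, x)² / C(40, 20) and d = (x − 10)/10:

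- P(x = 10) = 184756² / 137846528820 = 0.248
- P(x = 9 or 11) = 2 × 167960² / 137846528820 = 0.409
- P(x = 8 or 12) = 2 × 125970² / 137846528820 = 0.230

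So P(|d| ≥ 0.20) = 1 − 0.248 − 0.409 = 0.343, and P(|d| ≥ 0.30) = 0.343 − 0.230 = 0.113.

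The same calculation for other totals, hospitals equal in size:

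| Assumed N | SD of d | P(difference ≥ 20 points) | P(difference ≥ 30 points) |
|---|---|---|---|
| 30 | 0.19 | 0.47 | 0.14 |
| 40 | 0.16 | 0.34 | 0.11 |
| 60 | 0.13 | 0.20 | 0.02 |
| 100 | 0.10 | 0.07 | 0.003 |

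With 70% of patients at one hospital the chances are somewhat lower: 0.30 and 0.08 at N = 40. The expected signed difference is 0 in every case.

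**What an imbalance would do.** The shift in the unadjusted arm difference is d × (hospital effect). With an assumed hospital effect of 0.5 SD:

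- d = 0.20 gives 0.20 × 0.5 = 0.10 SD.
- d = 0.30 gives 0.30 × 0.5 = 0.15 SD.

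For scale, with 20 patients per arm the standard error of a difference in means is √(2/20) = 0.316 SD. A shift of 0.15 SD is therefore about half a standard error.

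**Type I error.** An unadjusted two-sample t-test was simulated with no treatment effect (N = 40 and 60, hospital effect 0.5 and 1.0 SD, 20,000 runs each). The rejection rate was 0.048 to 0.051 at the 5% level, and the mean estimated arm difference was at most 0.005 SD from 0.

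**Precision.** With equal hospitals, an effect of e SD adds e²/4 to a within-hospital variance of 1:

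- e = 0.5: 1 + 0.25/4 = 1.0625, so confidence intervals are wider by √1.0625 = 1.03.
- e = 1.0: 1 + 1/4 = 1.25, so they are wider by √1.25 = 1.12.

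**The case against.** The strongest reply is that unstratified allocation is a valid design, that the protocol states nothing false here, and that adjustment for hospital may sit in a statistical analysis plan that is not at hand. This stands in large part. It is why the point is an improvement and not an error. It does not reach the allocation procedure itself, whose place is the protocol.

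A second reply also has weight. Participants are examined before and after treatment, and the sample-size text is framed on change. In a change-from-baseline comparison a constant offset between hospitals cancels. The shifts and variance factors above then apply only to a hospital difference in the change itself.

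A reader might infer more than the text supports:

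- **That hospital is confounded with arm.** It is not. Under concealed individual randomisation hospital is independent of arm, the expected bias is 0, and the standard error already allows for chance imbalance.
- **That a single series is used for both sites.** The protocol does not say so. Separate lists per hospital would also fit its wording.
- **That envelope order, and so concealment, must break down across two sites.** The text has the research assistant carry out allocation. One person holding one series could keep strict order, so no failure is shown.
- **That operators, devices or sample handling differ between hospitals.** The protocol does not say who measures, with what device or where.
- **That a shift of 0.15 SD has a 26% chance.** That figure is the probability of a 13:7 split or worse among 20 patients at one hospital under simple allocation. The 0.15 SD shift needs a 30-point difference in hospital share, for which the chance at N = 40 is 11%.

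**Conclusion.** The point holds as a minor one. The protocol recruits at two hospitals, describes no stratification by hospital and no list or envelope set per hospital, and leaves hospital out of an explicit control list. The comparison is not biased in expectation and its type I error is intact.

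The cost is avoidable chance imbalance and some precision. At an assumed 40 patients in equal hospitals and arms, the chance is 34% for a difference in hospital share of at least 20 points and 11% for at least 30 points. The outcome variance is inflated by 1.06 to 1.25 if hospitals differ by 0.5 to 1.0 SD on the outcome analysed. The imbalance fades quickly with size: at 100 patients the two chances are 7% and 0.3%. The loss of precision does not depend on N.

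**What to change.** Before enrolment:

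- Generate one 1:1 list per hospital, in permuted blocks of varying size.
- Prepare a separate sequentially numbered opaque envelope set for each hospital, and say so in the protocol.
- Add hospital to the control variables and to the between-arm comparison. This belongs with the stratified lists, because an analysis that ignores hospital would not recover the precision that stratification makes available.

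If enrolment has already begun, leave the allocation as it is and add hospital to the comparison only.

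The cost is two short lists and one extra model term, which uses one degree of freedom. Blocking makes the last assignments in a block slightly predictable, and varying the block size limits this.

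### The Protocol gives investigators access to the randomisation sequences without limiting it to after assignment, which taken literally conflicts with the sealed-envelope concealment in the same paragraph

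*Protocol*

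**What the plan says.** All the relevant text but one item is in the Methods section of the Protocol. The trial is described as having a "single-blind parallel randomized controlled trial design", with 1:1 allocation from computer-generated random numbers. On concealment it says: "The random number results were entered into sealed envelopes using the SNOSE (sequentially numbered, opaque sealed envelopes) system". Participants are then assigned "based on the order of randomization (allocation concealment) carried out by the research assistant" and receive their irrigation packs. The paragraph closes with one sentence in two halves. The first half is "The investigators needed access to the blinding group's sequences". The second is that "the entire study team was instructed not to communicate with participants about their sequences".

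The opening of Methods says the study follows CONSORT "by clearly stating the items that must be informed in RCT research reports to avoid bias", and puts enrolment ahead of allocation in the participant flow. The remaining item is in the Background, which names cytokine mRNA expression as the primary outcome.

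**The concern.** Sealed envelopes conceal allocation only if the people who decide whether a patient enters the trial cannot learn the next assignment by another route. A statement that investigators need the sequences, with no limit on when, describes such a route. Someone who knows what comes next can, knowingly or not, hasten, delay or decline an entry, so that the arms differ before any treatment is given.

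A difference of that kind would carry into every between-arm comparison, including the primary mRNA outcome. Keeping participants unaware of their group would not repair it, because it arises before they have a group. What is at stake is therefore whether the concealment claim can be relied on. The single-blind design is a legitimate choice and is not the problem.

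**Working it through.** No arithmetic applies: the point depends on no sample size, variance, power or error rate. The check sets the statements side by side and asks which readings of the access sentence agree with the rest.

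**Inputs, all from Methods**

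| Element | What is stated | What is left open |
|---|---|---|
| Concealment device | Sequentially numbered, opaque sealed envelopes | Who holds the list behind the envelopes |
| Who assigns | The research assistant, in randomisation order | Whether this person also screens or enrols |
| Who has the sequences | The investigators, as a group | When, which of them, and for what purpose |
| Who screens and enrols | Nobody is named; enrolment appears only as a phase in the flow | Whether investigators do it |
| Limit on use of the sequences | The team does not discuss them with participants | Any limit on the team's own knowledge |
| Blinding | Single-blind | Which party is blinded |

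**Step 1: search for a limit on access.** In the Protocol text at hand, the words for investigators and for access each occur once, both in the access sentence. The plural word for the sequences occurs twice, both times in that same sentence. Statements limiting the timing, role or purpose of the access: 0.

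**Step 2: test the possible readings.**

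1. *A slip for having no access.* Consistent with the envelopes and with separate assignment by the assistant. But the text then says the reverse of what is meant about a main safeguard against bias.
2. *Knowledge of a participant's group after assignment.* Consistent with the envelopes and with the single-blind label. The second half of the sentence, which speaks of the participants' own sequences, also fits.
3. *Access to the list, including assignments not yet made.* This is the literal sense of unrestricted access to sequences. It is not consistent with concealment from anyone who both has that access and recruits.

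Nothing in the text excludes reading 3.

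**Step 3: ask whether the stated safeguards close the gap under reading 3.** Three are stated.

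- The envelopes stop someone from reading an assignment through or out of the packet. They do not stop someone who can see the list.
- Assignment by the research assistant separates the act of assigning from the investigators. It does not separate recruitment from the list, because the text does not say who recruits.
- The instruction not to tell participants protects the participants' blind only.

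None of the three limits what a recruiter may know beforehand.

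**The case against.** The best case on the other side is that context favours a harmless reading. The paragraph runs in order: numbers generated, envelopes filled, participants assigned, packs handed out, and only then investigator access. The sentence refers to blinding rather than to recruitment, and its second half is about the group a participant already holds. In a single-blind trial, investigators knowing the group after assignment is ordinary. The assistant is also named as a role distinct from the investigators. For harm to occur, access would have to come before assignment, cover future assignments, and belong to someone who recruits; the Protocol states none of these.

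Most of this stands. Readings 1 and 2 are as open as reading 3, and the envelopes and the assistant are real safeguards that deserve credit. A reader might infer from the sentence that concealment failed, or that the arms were selected. The Protocol does not support that: it shows an ambiguous statement, not a breach. A reader might equally infer that investigators and outcome assessors are meant to be unblinded after assignment. That is not established either, since the blinded party is not named and a slip for no access would mean the opposite.

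What does not stand is that the matter is one of style, or one that can be left to a statistical analysis plan. The text does not merely omit a detail. It makes a positive statement that, followed as written, can defeat the concealment claimed two sentences earlier. Who may see the sequence before assignment is a matter of trial conduct and belongs in the protocol.

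**Conclusion.** The point holds as a conflict in wording that should be corrected. Unrestricted investigator access, read literally, is incompatible with the stated concealment if anyone with that access screens or enrols, and the Protocol neither limits the access nor says who recruits.

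No size or direction of bias can be derived. The text at hand gives no sample size and names no recruiting staff. If nobody who can see the sequence before assignment screens or enrols, the bias from this source is zero. The conclusion rests on two observations: no limit on access appears in the text shown, and the literal reading cannot be excluded from it. Confidence is moderate, because two harmless readings remain open.

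**What to change.** Replace the access half of the sentence with: *No one who screens or enrols participants has access to the randomisation sequence before assignment; each envelope is opened only after eligibility and consent are recorded.* Keep the instruction not to tell participants.

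Separately, the sponsor should state whether investigators and outcome assessors know a participant's group after assignment. The replacement sentence leaves this open on purpose: if no access was the intended meaning, wording that grants knowledge after assignment would weaken the blinding. As it stands, it fits both harmless readings and excludes only the harmful one.

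The paragraph is written in the past tense, which may mean that randomisation has already taken place. In that case new text cannot restore concealment, and the sponsor should report who had access to the sequence and when.

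The cost is small: one sentence of text, and keeping the list away from the staff who recruit. The envelopes and the research assistant are already in the plan. If the list is now held by someone who also recruits, it has to be passed to someone who does not. The single-blind design is unchanged.

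### The sample size rests on a before/after paired t-test formula, which does not size the randomised comparison of extract plus saline with saline alone

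*Protocol*

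**What the plan says.** In the Protocol, Methods, the paragraph after the exclusion criteria gives the only statement on sample size. The formula used is one for "the change in the average (mean) before and after the intervention of the two paired groups tested with paired t-test". No resulting number and no inputs follow.

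Elsewhere the Protocol describes a different structure:

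- Methods calls the study "a single-blind parallel randomized controlled trial design".
- Participants are allocated individually, from sequentially numbered sealed envelopes, by "random numbers generated by a computer program and statistical software with an allocation of 1:1".
- The list of variables in Methods makes the treatment received (saline with extract, or saline alone) the independent variable.
- Background states the purpose of the extract as "to increase the results of 0.9% NaCl nasal wash by assessing mRNA expression", and names IL-4, IL-6, IL-13 and TNF-α as the primary outcome.
- The key to Figure 1 lists two examinations before treatment (for example "O1 = Examination before treatment") and two after it.

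**The concern.** A paired t-test formula sizes a study to detect a mean change within the same people. In this trial that change would combine any effect of the saline wash itself, regression to the mean and the passage of time with any effect of the extract. Only the contrast between randomised arms isolates the extract, and its precision follows a different formula.

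If the calculation was done as described, the number of participants says nothing direct about the chance of detecting an extract effect. A null result could not be interpreted. There would also be a temptation to rely on a before/after change within the extract arm, which randomisation does not protect.

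**Working it through.** **There is no figure to reproduce.** The Protocol states no N, SD, effect, alpha, sidedness, power or dropout. What can be checked is whether the named formula fits the design, and how far the two formulas differ.

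**Fit with the design.** A paired test needs paired observations. Two kinds of pairing are conceivable:

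1. *Pairs across arms.* Methods describes individual allocation by numbered envelope, with no matching and no crossover. There are no such pairs.
2. *Before and after within a patient.* These pairs exist, but testing them answers whether an arm changed, not whether the arms differ.

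The comparison that was randomised is therefore a two-independent-group comparison, whether of change or of baseline-adjusted post-treatment values.

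**Size of the mismatch (illustrative).** Assumptions, none of them from the Protocol: two-sided alpha 0.05; 80% power; the same SD of change, s, in both arms; a between-arm difference equal to the within-arm change, δ; normal approximation.

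- Paired: n = ((1.960 + 0.842)·s/δ)², so the noncentrality is 2.802.
- Two independent arms, change scores: n per arm = 2·((1.960 + 0.842)·s/δ)². This is 2.0 times the paired n in each arm, and 4 times in total.

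Using the paired n for the between-arm test:

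| Use of the paired n | Noncentrality | Power | Detectable difference at 80% power, relative to δ |
|---|---|---|---|
| Per arm | 2.802/√2 = 1.981 | Φ(1.981 − 1.960) = 0.508 | √2 = 1.41 |
| Trial total | 2.802/2 = 1.401 | Φ(1.401 − 1.960) = 0.288 | 2.0 |

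**Check with exact t distributions.**

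- δ/s = 0.5: 34 paired, against 64 per arm.
- δ/s = 0.3: 90 paired (power 0.804), against 176 per arm. Between-arm power is 0.517 with 90 per arm and 0.291 with 90 in total.

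**Baseline adjustment.** With equal pre- and post-treatment variances and correlation ρ, ANCOVA variance is (1 + ρ)/2 times the change-score variance. With the paired n in each arm the noncentrality is therefore 2.802/√(1 + ρ):

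| Assumed ρ | Power |
|---|---|
| 0 | 0.800 |
| 0.3 | 0.690 |
| 0.5 | 0.628 |
| 0.7 | 0.575 |

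**If saline also improves patients.** Suppose the between-arm difference is only half the within-arm change (assumption). With the paired n in each arm and unadjusted change scores, power is about 17%.

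**The case against.** The strongest reply is that the sentence is loosely worded. The Figure 1 key fits two arms, each examined before and after treatment. The author may have meant a comparison of change between arms and mislabelled the test. The calculation actually done, perhaps set out in a statistical analysis plan not seen here, could then be a proper two-group one. This reading is plausible, and it limits the finding to the text: an error in the calculation itself is not shown. It does not rescue the sentence, because comparing change between two arms is still not a paired t-test. A two-group calculation elsewhere would contradict the Protocol, which would still need correcting.

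It is also fair to say that the power figures are generic. Nothing in the Protocol supports equating the between-arm difference with the within-arm change, or says whether the formula's n is per arm or in total. The figures show how the two formulas relate and do not estimate this trial's power. The equality assumption is, if anything, generous, because the comparator is itself a saline wash and may also produce improvement.

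**Conclusion.** The concern holds. The Protocol's only stated basis for the number of participants is a formula for a within-patient change, whereas the trial randomises patients 1:1 to two independent arms in order to compare them. This is a statement that is wrong as written, not a detail left for the analysis plan.

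Under the assumptions above, unadjusted change scores need twice the paired n in each arm. A nominal 80% becomes about 51% (n per arm) or 29% (n in total). With n per arm, baseline adjustment softens the loss to between 69% and 57% for correlations of 0.3 to 0.7, and removes it at correlation 0. Whether the planned enrolment is adequate is unknown.

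**What to change.** Replace the sample-size sentence in Methods with wording such as:

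> The sample size is calculated with the formula for two independent groups (1:1) for the between-arm difference (0.9% NaCl plus extract versus 0.9% NaCl) in mRNA expression of [one named cytokine], using a difference of [ ], an SD of [ ], two-sided alpha of [ ] and power of [ ].

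If the calculation relies on baseline adjustment, which would be the more efficient choice, add the assumed correlation between pre- and post-treatment values. Then state the power, or the detectable between-arm difference, at the planned enrolment.

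One cytokine has to be named because the calculation needs a single SD and difference. The analysis model and the handling of the other three cytokines can stay with the statistical analysis plan.

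The cost is one sentence and one recalculation. The correction does not itself require more participants, but the stated power or detectable difference will probably look less favourable, and the sponsor must decide which cytokine drives the number.
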